5.2 Subject disposition

See mock TFLs.

5.3 Primary endpoint analysis

Refer to SAP for confirmatory analyses cut-off version 5.

5.4 Secondary endpoint analysis

Refer to SAP for confirmatory analyses cut-off version 5.

5.5 Exploratory efficacy endpoints analysis

5.5.1 Bleed-related assessments

The assessments related to bleeding episodes are defined in section 6.2, and will be addressed by use of the FAS and the "On-treatment without ancillary therapy excl. data before restart" analysis dataset as described in section 5.1.

In the SAP for the confirmatory analyses cut-off version 5, the bleeding episode related endpoints (including the primary endpoints and supportive secondary efficacy endpoints) are only defined for

the on-demand treatment in arm 1 and until the confirmatory analyses cut-off in arm 2. In this SAP, they will also be assessed for arm 1 after concizumab treatment is initiated and for arm 2-4 until the 56-week cut-off. The confirmatory secondary endpoints for intra-patient comparison had been concluded at the confirmatory analyses cut-off therefore will not be repeated again at the 56-week cut-off.

The number of treated spontaneous and traumatic bleeding episodes as event/count data will be presented using descriptive statistics as described in section 5.1, and by cause of bleeding episodes (Spontaneous, Traumatic, Surgical), anatomical location of bleeding episodes (Target joints, Joints, Muscular, Skin, Gastrointestinal, Mouth-gums-nose, Urinary system, Central nervous system, Other), classification of bleeding episodes (Mild/moderate, Severe) and location of severe bleeding episodes,

Furthermore, an ABR will be calculated at an individual basis as

$$ABR = \left(\frac{\text{Number of treated spontanous or traumatic bleeding episodes}}{\text{Number of days in the analysis data set}}\right) x 365.25$$

These continuous assessments will be presented using descriptive statistics as described in section 5.1,

The descriptive statistics for the bleeding episode related assessments up until week 56 will be presented by treatment arms and 'Total concizumab'. Furthermore, it will be presented by haemophilia types (HA, HB).

5.5.2 Pharmacokinetic and pharmacodynamic assessments

The assessments related to PK and PD are defined in section 6.2, and will be addressed by use of the SAS and the "On-treatment without data before restart" analysis dataset as described in section 5.1.

The full 24-hour PK/PD profiles were measured at Visit 2a and Visit 9a, which were already presented at the confirmatory analyses cut-off and will not be repeated again at the 56-week cut-off. In this SAP, only pre-dose PK/PD assessments up till 56-week cut-off will be presented.

All PK and PD endpoints and assessments are continuous and will be presented using the descriptive statistics as described under section 5.1.

5.6 Exploratory safety analyses

For arm 2 patients who were randomised before the treatment pause and who restarted in arm 4, all the safety data collected while on concizumab will be presented as arm 4 data.

5.6.1 Extent of exposure

A summary showing patients that escalate, deescalate, or remain on the 0.20 mg/kg/day dose will be presented separately for HA and HB.

The length of the periods constituting the analysis data sets will be presented descriptively.

5.6.2 Adverse events

All exploratory safety endpoints are defined in section 6.2.

All adverse events will be coded using the current version of MedDRA. Hypersensitivity reactions, medication errors and injection site reactions are categorised in the CRF as AEs requiring additional data collection. Additional information on these events will be collected using separate forms. Further, a MedDRA search will also be used to define these events. Thromboembolic events are defined and categorised as AESIs.

Adverse events will be evaluated using descriptive statistics based on the analysis data sets as described in section 5.1. The outputs will differentiate between haemophilia type.

Furthermore, for the on-treatment analysis data set the outputs on adverse events will also include information on

- System organ class
- Severity (mild/moderate/severe), seriousness (serious/non-serious) and relation to treatment (possibly/probably/unlikely)
- Adverse events leading to drug discontinuation
- Most frequent adverse events (occurring in more or equal to 5% of patients)
- Deaths
- Medication errors

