No significant thromboembolic events or signs of DIC were reported in the phase 1 or phase 2 concizumab clinical trials with an exposure time of up to 102 weeks for the individual patient in the phase 2 trials. After initiation of the phase 3 clinical trials, 5 serious thromboembolic events (all non-fatal) were reported in 3 patients; the events were of different pathological aetiology, i.e. arterial and venous. All events occurred within 3 months of concizumab treatment initiation. All 3 patients experiencing thromboembolic events had different types of thromboembolic risk factors and all 3 patients had used breakthrough bleed treatment just before the onset of symptoms for the thromboembolic event. In 2 of the cases, either a relatively high dose or prolonged treatment with factor product was reported. The concizumab exposure levels for these 2 patients were also among the highest levels observed across the phase 2 trials (4310 and 4255) and the phase 3 trials (4307 and 4311), and it was also noted that overall, the concizumab exposure levels in phase 3 at the 0.25 mg/kg dose-level were higher than expected. For the remaining patient, a possible/potential renal infarct prior to trial entry is being assessed (not confirmed). The findings from the investigations of the cases have led Novo Nordisk to make several changes to the trial protocols to reduce the risk that additional patients treated with concizumab will experience thromboembolic events.

These changes include:

- A new guidance for treatment of mild and moderate breakthrough bleeds, with specific guidance for use of the lowest dose of factor product or bypassing agent while on concizumab PPX (see Section 5.2.3).
- That patients **must** contact the site when they have a suspected bleed (see Section 5.2.3).
- Continuation of previous PPX for up to two weeks after initiation of concizumab dosing is no longer allowed (see Section 5.2.1)

• A new concizumab dosing regimen including an initial daily dose of 0.20 mg/kg concizumab (instead of 0.25 mg/kg). Criteria for an increase or decrease in the daily maintenance dose to 0.25 mg/kg or 0.15 mg/kg, respectively (based on concizumab exposure levels at the week 4 visit) are provided. The loading dose remains 1.0 mg/kg (see Section 5.2.1).

- Elective major surgery is no longer allowed (see Section 9.9).
- Trial stopping rule requiring urgent evaluation by the Novo Nordisk Safety Committee and

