9.3.1 Time period and frequency for collecting AE and SAE information

All AEs will be collected from the first trial-related activity after obtaining informed consent and until end of trial visit, at the time points specified in the flowchart.

All SAEs will be recorded and reported to Novo Nordisk or designee within 24 hours, as indicated in Appendix 5 for the IMP and on demand treatment, and in Appendix 8 for the investigational medical device. The investigator must submit any updated SAE data to Novo Nordisk within 24 hours of it being available.

Investigators are not obligated to actively seek for AE or SAE in former trial patients. However, if the investigator learns of any SAE, including a death, at any time after a patient has been discontinued from/completed the trial, and the investigator considers the event to be possibly/probably related to the investigational trial product or trial participation, the investigator must promptly notify Novo Nordisk.

Status: Page: Final

72 of 138

The method of recording, evaluating and assessing causality of AE and SAE and the procedures for completing and transmitting SAE reports are provided in Appendix 5 for the IMP and on demand treatment, and in Appendix 8 for the investigational medical device.

Timelines for reporting of AEs, including AESIs are listed in Figure 4.

Some AEs require additional data collection via a specific event form. This includes medication errors observed during the trial. The relevant specific events are listed in Table 13 and the reporting timelines in Figure 4.

[figure not shown]

Figure 4 Decision tree for determining the event type and the respective forms to complete with associated timelines

Table 13 AEs requiring additional data collection (via specific event form) and AESIs^a

Event type	AE requiring additional event form	AESI
Thromboembolic events		X
Hypersensitivity reaction	X	
Injection site reaction	X	
Medication error	X	

^aRefer to Section 9.3.6 for reporting details

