Definition of a Transient Ischemic Attack: The definition of Transient Ischemic Attack is according to the American Heart Association/American Stroke Association. A Transient ischemic attack (TIA) is a transient episode of neurological dysfunction caused by focal brain, spinal cord or retinal ischemia, without acute infarction.³³

F) Definition of deep vein thrombosis:

The "Clinical Practice Guideline from the American Academy of Family Physicians and the American College of Physicians" on diagnosis of venous thromboembolism recommends ultrasound scanning for patients with intermediate or high pre-test probability of deep vein thrombosis (DVT) in the lower extremities. Accordingly, venous thrombosis should be demonstrated by compression ultrasound, duplex ultrasound, colour Doppler imaging or venography (phlebography).

G) Definition of other clinically significant thromboembolic events:

Signs or suspicion of a clinically significant thromboembolic event (e.g. visceral arterial embolus/thrombus, extremity arterial embolus/thrombus or portal venous thrombosis). Superficial thrombophlebitis related to a central venous access device is not considered a clinically significant thromboembolic event unless evaluated as such by the investigator.

CONFIDENTIAL

 Date:
 25 March 2021
 Novo Nordisk

 Version:
 5.0

 Status:
 Final

 Page:
 114 of 138

H) Definition of peripheral artery occlusion:

Clinical signs of acute arterial occlusion verified by ankle-brachial index (ABI) test, Doppler and ultrasound (Duplex) imaging, computerised tomographic angiography, Magnetic Resonance Angiography (MRA) or conventional angiography. The 2011 American College of Cardiology Foundation/American Heart Association Focused Update of the Guideline for the Management of Patients with Peripheral Artery Disease could serve as a reference for the diagnosis of lower extremity peripheral artery disease

AEs requiring additional data collection

AEs requiring additional data collection are AEs where the additional data will benefit the evaluation of the safety of the trial product.

Hypersensitivity type reactions:

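### SAP 5.6.2 states a MedDRA search for three adverse event types but none for thromboembolic events, so an event not classified as an AESI could be left out of the thromboembolic count

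*SAP*

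**What the plan says.** SAP 5.6.2 starts from a common base: "All adverse events will be coded using the current version of MedDRA". It then treats two groups of events differently.

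- Three event types: "Hypersensitivity reactions, medication errors and injection site reactions are categorised in the CRF as AEs requiring additional data collection". Separate forms collect extra information on them.
- The second route for those three, and the rule for thromboembolic events, stand in adjacent sentences: "Further, a MedDRA search will also be used to define these events. Thromboembolic events are defined and categorised as AESIs". The search terms are not given, and no search is mentioned for thromboembolic events.

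Protocol Section 9.3.1, Table 13, makes the same division: thromboembolic events are marked as AESIs and the other three as events needing an additional form. Section 9.3.1.1 gives an open-ended list of thromboembolic AESIs and requires each to be filed on an AE form and a safety information form. Appendix 5 sets out definitions for DIC, TMA, myocardial infarction, pulmonary embolism, stroke, deep vein thrombosis, other clinically significant events and peripheral artery occlusion.

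The number of thromboembolic events is a supportive secondary safety endpoint (protocol Section 4.3.2.2) and an assessment at the 56-week cut-off (SAP 6.2).

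**The concern.** Protocol Section 3.2 reports 5 serious thromboembolic events in 3 phase 3 patients, 2 of them in this trial, and says that clinical development was paused because of them. Yet SAP 5.6.2 gives a second route of identification to injection site reactions and states none for this risk.

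The thromboembolic count therefore appears to rest on classification at the site. The list is open-ended, one category turns on clinical significance, and the trial is open-label (protocol Section 7.3), so classification is made with treatment known. The committees described in protocol Appendix 4 are an internal safety committee and a data monitoring committee; neither is described as adjudicating events. With counts this small, one event in or out of the table changes how it reads.

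**Working it through.** The SAP gives no figure to reproduce here. The check is a comparison of passages, followed by an illustrative calculation.

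**Step 1: what the search covers.** In SAP 5.6.2 the search sentence follows the sentences on the three event types with extra data collection, and comes before thromboembolic events are mentioned. Its reference is back to those three. Table 13 of the protocol draws the same line, so this is not a slip of wording. No other supplied section mentions a MedDRA search.

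**Step 2: where an unclassified event would go.** Protocol Section 9.3.1 states: "All AEs will be collected from the first trial-related activity after obtaining informed consent and until end of trial visit". All are coded under SAP 5.6.2. So a thromboembolic event filed as an ordinary AE would still be in the database with its MedDRA term, and would fall within the planned outputs by system organ class, severity, seriousness and relation to treatment and, where applicable, discontinuation or death. It could be absent from the thromboembolic count.

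**Step 3: whether those outputs replace the count.** Not fully. The table of frequent events needs at least 5% of patients; on 158 patients that is 0.05 × 158 = 7.9, so 8 patients. System organ class tables would not bring together events in different organs, such as infarction, stroke and deep vein thrombosis.

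**Step 4: what one patient is worth (illustration only).** Inputs: 2 affected patients in this trial before the pause (protocol Section 3.2), and 158 expected patients (protocol Section 5.1), taken here as an assumed denominator. The exact 95% limits for x of n are:

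- lower = 2.5% quantile of Beta(x, n − x + 1)
- upper = 97.5% quantile of Beta(x + 1, n − x)

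| Patients affected | Proportion | Exact 95% limits |
|---|---|---|
| 2/158 | 1.3% | 0.15% to 4.50% |
| 3/158 | 1.9% | 0.39% to 5.45% |
| 4/158 | 2.5% | 0.69% to 6.35% |

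One more patient raises the upper limit by 5.45 − 4.50 = 0.95 or 6.35 − 5.45 = 0.90 percentage points. This shows what a single hypothetical omission would do. It does not estimate how many omissions there would be.

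**The case against.** The case on the other side is substantial.

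- **The SAP does not say that AESI filing is the sole route.** A reader might infer that unflagged events are simply missed. The text neither says so nor excludes a search, and SAP Section 1 places derivation detail in the ADRG and output specifications in the mock TFLs. Neither was supplied. This stands.
- **A miss needs a site error.** Appendix 5 gives written definitions and AESI reporting is mandatory. A significant event triggers treatment discontinuation (protocol Section 8.1) and urgent safety committee evaluation (Section 9.3.9), and a data monitoring committee reviews accumulating data. This makes an omission less likely, but it is not a term-based check of the count.
- **The asymmetry may have a reason.** Hypersensitivity and injection site reactions are described mainly by open-ended signs and symptoms, where a term search helps more. This is plausible, but the SAP does not give it as the reason.
- **Direction of error.** A reader might infer that the count is biased low. The documents do not support that. Category G of Appendix 5 takes in signs or suspicion of an event, and the stroke definition includes intracerebral and subarachnoid haemorrhage, so the AESI rule can add events as well as lose them. The net direction is unknown.
- **The renal infarct in protocol Section 3.3.** It is tempting to read "a possible/potential renal infarct prior to trial entry is being assessed (not confirmed") as an example of a missed event. It preceded trial entry, and the patient is already among the 3 with reported events. It shows nothing about on-trial ascertainment.
- **Investigator discretion in Appendix 5.** The words "is not considered a clinically significant thromboembolic event unless evaluated as such by the investigator" concern only superficial thrombophlebitis related to a central venous access device. They are one narrow exclusion, not a general licence.
- **The denominator.** 158 is planned enrolment. The safety analysis set is everyone exposed to concizumab or randomised to on-demand treatment, including before the pause. The percentage of patients is a planned summary under SAP 5.1, but these limits remain illustrative.

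**Conclusion.** The point holds as a gap in the stated method. SAP 5.6.2 specifies a second, term-based route for three adverse event types and states none for the event type that led to the pause. A thromboembolic event that a site did not classify as an AESI could be left out of that count while remaining in the coded data and the general summaries.

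The size cannot be estimated, because the documents give no rate of unclassified events and no measure of how complete AESI classification is. The shift of about 0.9 percentage points in the upper limit per patient rests on the assumed denominator of 158 and a hypothetical omission.

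The conclusion is confined to this SAP, which is descriptive and supports no further confirmatory conclusions. How the confirmatory SAP identifies these events cannot be seen. The change is still worth making because it is cheap and uses data that will already be coded.

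**What to change.** In SAP 5.6.2:

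1. Keep the AESI-based count as the main thromboembolic count.
2. Add a prespecified MedDRA search of embolic and thrombotic terms, including DIC and TMA, as a cross-check, with the term list fixed in advance.
3. Report both counts.
4. List every search hit not classified as an AESI, with medical review of each against the Appendix 5 definitions.

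If the ADRG or mock TFLs already specify this, a cross-reference is enough.

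The cost is one SAP sentence, one table and a few medical reviews; no new data are needed. The downside is that some hits, such as device-related superficial thrombophlebitis, will be events that the protocol excludes. That is why the search should be a cross-check and not replace the main count.

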5.6.3 Additional safety assessments

Assessments in relation to planned safety laboratory measurement, body measurements, vital signs and physical examinations are defined in section $\underline{6.2}$. The assessments will be presented using descriptive statistics as described in section $\underline{5.1}$. Number of patients with a positive antibody test will be presented as described in section $\underline{5.1}$ and furthermore a list of all positive antibodies recorded during the trial will be presented.

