- patients who previously participated in NN7415-4255 (explorer 5)
- patients who were in screening phase at the time of the pause
- patients entering from NN7415-4322 (explorer 6)
- new patients coming from outside the concizumab programme.

All of the above-mentioned new patients will start the trial at visit 1a (screening visit).

5.0 Final 42 of 138

Note: ^aThe individual maintenance dose will be either 0.15, 0.20 or 0.25 mg/kg concizumab (see Section 9.2.2); ^bAdditional patients on OnD treatment or patients on PPX with factor replacement, patients from explorer5 enrolled *after* the treatment pause and patients randomised to arms 1 or 2 *before* the treatment pause.

Abbreviations: OnD = on demand; PPX = prophylaxis; V = visit

Figure 1 Trial design

The randomisation between the treatment arms 1 and 2 will be stratified according to haemophilia type and bleeding frequency during the 24 weeks prior to screening; see Section 7.2.

Treatment arms 1 and 2:

Approximately 60 patients (24 HA and 36 HB patients), previously treated on-demand, will be randomised 1:2 to no prophylaxis versus concizumab prophylaxis.

Patients randomised to arm 1 before the pause were instructed to continue their on demand treatment and report data until trial restart. Patients who were randomised to arms 1 and 2 prior to the treatment pause should re-enter the trial in arm 4. Instead 60 new patients will be identified to be randomised into arms 1 or 2.

Treatment arm 3:

The HA patients enrolled into the concizumab phase 2 trial NN7415-4255 (explorer 5) were offered enrolment into arm 3. These patients continued concizumab PPX and had a combined visit 1 and 2. Upon trial restart, these patients will receive the new concizumab dosing regimen. After the initial dose adjustment period, patients will receive at least 24 weeks of treatment on their final maintenance dose (main part). Subsequently, these patients will be offered up to 128 weeks of concizumab PPX (extension part).

Patients who were in NN7415-4255 (explorer 5) at the time of the treatment pause, and who have now completed explorer 5, will be offered screening in this trial and should enter arm 4 (visit 1a) as outlined below.

Page:

43 of 138

Treatment arm 4:

Arm 4 will include at least 60 patients (30 HA and 30 HB patients) previously on prophylaxis with factor products with a minimum of 24 weeks observation in NN7415-4322 (explorer 6).

In addition, arm 4 will also include:

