9.4.7 Immunogenicity assessments

Samples for the determination of anti-drug antibodies will be collected according to the flowchart in Section 2. All patients will have samples drawn at V1/V1a, but only patients randomised/allocated to concizumab treatment (arms 2, 3 and 4) will have samples drawn at the remaining indicated timepoints in the main part of the trial. In the extension part of the trial, samples must be drawn for all patients (arms 1–4). Sampling should always take place prior to administration of concizumab. In case of suspected hypersensitivity reaction requiring systemic treatment, additional blood samples are to be collected; refer to Section 9.4.8.

Assessment of binding antibodies against concizumab (anti-drug antibodies (ADA) will be performed at specialised laboratories whereas assessment of neutralising antibodies will be performed at Novo Nordisk.

Analysis for ADA will be done with a bridging ECL assay (binding ADA assay) using labelled concizumab for antibody capture and detection. If a sample is confirmed positive in the confirmatory assay, the sample is considered positive for binding antibodies. Confirmed positive

samples will be characterised in a specificity assay for binding to IgG backbone or the S241P mutation. Furthermore, positive samples will be characterised for neutralising activity using a neutralising ADA assay. All antibody assays are validated according to international guidelines and recommendations.

The following data will be available:

- Anti-concizumab antibodies
- Anti-concizumab antibody titres
- Anti-concizumab binding antibodies cross-reacting with IgG4 backbone or S241P mutation
- Anti-concizumab neutralising antibodies

The samples will be analysed and reported to sites at the confirmatory analyses cut-off and at end of extension part (end of trial). A detailed description of the assay methods will be included in the antibody analysis report at the end of the trial.

Patients positive for binding antibodies at end of follow-up may be followed outside this protocol.

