CONFIDENTIAL

Date: Version: Status: Page:

04 August 2022 | Novo Nordisk Final 13 of 29

Statistical analyses 5

General considerations 5.1

This SAP will address the details of the descriptive statistics implemented on all arms (1, 2, 3 and 4) at the 56-week cut-off of trial NN7415-4307. The 56-week cut-off is defined as when all patients in arms 2, 3 and 4 have completed visit 13a (or permanently discontinued treatment).

In general, all TFLs will differentiate between HA and HB patients. For some endpoints/assessments HA and HB may be pooled.

Unless specified otherwise, the endpoints/assessments will be presented using the analysis sets as displayed in Table 1.

Table 1 Analysis sets used for analyses and/or presentations of endpoints/assessments

Endpoint/assessment categories ^a	Subject Analysis Set	Analysis Data Sets
Bleeding episodes	FAS	On-treatment without ancillary therapy excl. data before restart
PK, PD and safety not relating to events	SAS	On-treatment without data before restart
Safety relating to events ^b	SAS	On-treatment and On-treatment without data before restart

^aWhich endpoints/assessments that belong under each category can be found in section 9 of the protocol version 5. ^bThis specifically refers to: number of thromboembolic events, number of hypersensitivity type reactions, number of injection site reactions, number of patients with antibodies to concizumab, and number of adverse events.

Continuous endpoints/assessments will be presented using descriptive statistics which will include min, max, mean, SD, median, and quartiles. For PK endpoints/assessments, the descriptive statistics will also include geometric mean and CV. Event data (including AEs) will be summarised including number of patients with an event/episode, percentage of patients with an event/episode, number of events/episodes and rate of events/episodes. Categorical assessments will be summarised by number and percent of patients in each category.

Presentations of results will be by arm and visit (when applicable) and when relevant arm 1 will be split into two parts with on-demand treatment and concizumab treatment.

Event data relating to safety where the 'on-treatment' analysis data set is used will include both data on the initial and the new concizumab dosing regimen.

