Assessment	Number of hypersensitivity type reactions	Concizumab (arm 1) • From start of the new	Count	until week	56 cut-off will be prese	ented.	5.6.2
Assessment	Number of injection site reactions	concizumab dosing regimen up until week 56 cut-off	Count				5.6.2
		 Concizumab (arms 2-4) Before the pause: From start of concizumab treatment (week 0) up until 					

SAP NN7415-4307 week 56 | 25 of 29

Statistical Analysis Plan W56 Trial ID: NN7415-4307			Date: Version:	04 August 2022 1.0	Status: Final Page: 26 of 29	Novo Nordisk
		7 weeks after the treatment pause as well as • After the pause: From start of the new concizumab treatment (week 0) up until week 56 cut-off				
Assessment	Number of patients with antibodies to concizumab	 Concizumab (arms 2-4) From start of the new concizumab dosing regimen (week 0) up until week 56 cut-off 	Count	from arm 2-	at-off is when all patients -4 have completed visit 13a ntly discontinued treatment.	5.6.3
Assessment	Change in <safety laboratory="" parameter=""></safety>	 On demand (arm 1) From randomisation to on demand treatment after the pause up until start of concizumab treatment Concizumab (arm 1) From start of the new concizumab dosing regimen up until week 56 cut-off Concizumab (arms 2-4) From start of the new concizumab dosing regimen up until week 56 cut-off 	Multiple units	each safety haematolog coagulation 19 of the pr Week 56 cu from arm 2- or permaner Concizuma	pratory parameter> refers to laboratory parameter for y, biochemistry and parameters as listed in table otocol version 5. At-off is when all patients 4 have completed visit 13a ntly discontinued treatment. b (arm 1) data available up 56 cut-off will be presented.	5.6.3

SAP NN7415-4307 week 56 29

Statistical Analysis Plan W56 Trial ID: NN7415-4307		UTN: U1111-1225-9722 EudraCT No.: 2018-004891-36	Date: Version:	04 August 2022 1.0	Status: Fina Page: 27 of 29	
		From start of treatment after the pause (week 0) to every visit where the <safety laboratory parameter> is planned to be measured up until V13a (week 56)</safety 				

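### The 56-week antibody count ignores antibody status before the first dose of the new regimen, so antibodies persisting from earlier concizumab exposure can be counted under that regimen in arms 3 and 4

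*SAP*

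**What the plan says.** SAP section 5.6.3 gives the rule in one sentence: "Number of patients with a positive antibody test will be presented", following section 5.1, and in addition "a list of all positive antibodies recorded during the trial will be presented".

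The antibody row of SAP Appendix 2 covers arms 2-4 only, with the time frame "From start of the new concizumab dosing regimen (week 0) up until week 56 cut-off".

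SAP section 5.1, Table 1 with its footnote b, assigns the antibody count to two data sets: "On-treatment and On-treatment without data before restart". Section 5.1 adds that event data in the first of these "will include both data on the initial and the new concizumab dosing regimen". The second, called the restart-only data set below, drops observation time before restart (SAP section 4).

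On earlier exposure, protocol section 5.1 says of arm 3: "The HA patients enrolled into the concizumab phase 2 trial NN7415-4255 (explorer 5) were offered enrolment into arm 3". It describes those patients as having continued concizumab prophylaxis. Arm 4 takes, besides patients from the non-interventional study, those randomised to arms 1 or 2 before the pause, later phase 2 completers, and on-demand patients added after arms 1 and 2 close. Patients allocated to arm 4 before the pause return to it.

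On sampling, protocol section 9.4.7 says "All patients will have samples drawn at V1/V1a" and lists "Anti-concizumab antibody titres" among the available data. The flowchart (protocol section 2) adds a visit 2a sample for arms 2-4 and a sample at visit 9a.

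**The concern.** A count of patients with antibodies on a regimen is normally read as the immunogenicity of that regimen. That reading needs a reference to status before dosing. Without one, the count can combine antibodies induced by the new regimen with antibodies that were already present. The mix can differ by arm: arm 2 after restart consists of newly randomised patients, arm 3 is wholly pre-exposed, and arm 4 is a mixture.

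The antibody count is a supportive secondary safety endpoint (protocol section 4.3.2.2). Protocol section 3.3 names immune complexes of concizumab and antibodies against it as a potential risk. A table that cannot separate new from carried-over antibodies is less useful for judging that risk.

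**Working it through.** The plan states no antibody rate, so there is no figure to reproduce. The check has three parts.

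**1. Is there a baseline condition anywhere in the supplied text?**
- SAP 5.6.3 counts positive tests and sets no condition on earlier status.
- SAP 5.1 defines a baseline after the pause (the latest measurement before the start of the new regimen) but does not apply it to antibodies.
- SAP Appendix 2 analyses safety laboratory values, weight, blood pressure and pulse as change. The antibody row is a plain count.
- None of these sections defines treatment-emergent or treatment-boosted antibodies.

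**2. What does the rule do to a positive patient?** Under the rule as written:

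| Situation | Restart-only data set | On-treatment data set |
|---|---|---|
| Negative before restart, positive afterwards | Counted | Counted |
| Antibody formed in this trial before the pause, still present after restart | Counted under the new regimen | Counted, but this set openly pools both regimens |
| Antibody formed in the phase 2 trial, still present on treatment here | Counted | Counted |
| Positive only before dosing, cleared by the first on-treatment sample | Not counted | Not counted |

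The second row (restart-only data set) and the third row (both data sets) are the problem.

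**3. How many patients could be affected?** Inputs are 60 randomised patients, 40 of them in arm 2 (16 HA + 24 HB); a planned minimum of 10 in arm 3; at least 60 prophylaxis patients in arm 4 (protocol section 5.1, Table 2); and up to 98 in arms 3 and 4 together (protocol section 5.3).

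- Planned total: 60 + 98 = 158, which agrees with the protocol.
- Arms 2-4: 40 + 98 = 138.
- Pre-exposed, planned minimum (arm 3 alone): 10, and 10/138 = 7.2%.
- Illustrative case, in which everyone in arms 3 and 4 outside the 60 prophylaxis patients was exposed: 98 - 60 = 38, and 38/138 = 27.5%. This is not a bound. Some of the 38 were never exposed (former on-demand patients), and some of the 60 may have been dosed in arm 4 before the pause.
- Ceiling: 98, and 98/138 = 71.0%.

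The share of pre-exposed patients with a persisting antibody is not in the documents. Taking 5%, 10% and 25% purely as assumptions, the expected number is n × p and the chance of at least one is 1 - (1 - p)^n:

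| Pre-exposed n | 5% | 10% | 25% |
|---|---|---|---|
| 10 | 0.5 (40%) | 1.0 (65%) | 2.5 (94%) |
| 38 | 1.9 (86%) | 3.8 (98%) | 9.5 (>99.9%) |
| 98 | 4.9 | 9.8 | 24.5 |

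Cells give expected carried-over positives, with the chance of at least one in brackets where calculated. They show how the count responds to the assumptions and do not estimate this trial's result.

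**The case against.** The case on the other side has real substance.

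- **The window is limited.** A reader might infer that any positive test at any time is counted. The documents do not support that: the count is confined to on-treatment periods, so carry-over requires persistence. This stands.
- **One presentation claims nothing about the new regimen alone.** The on-treatment data set is declared to pool both regimens. This stands for antibodies formed in this trial before the pause. It does not deal with antibodies formed in phase 2.
- **Output is by arm, and all positives are listed.** Arms 2 and 3 can therefore be told apart, and recorded pre-dose positives should be traceable by hand. This stands in part. Presentation by arm does not separate exposed from unexposed patients within arm 4. A list of positives does not give the number of baseline-negative patients, so no seroconversion proportion follows from it.
- **The protocol endpoint is itself a plain count, and the 56-week analysis is descriptive.** This stands and limits the consequence. It does not make the count easier to interpret.
- **A rule may exist elsewhere.** The analysis data reviewer's guide, the mock outputs and the SAP for the confirmatory cut-off were not available. If one of them holds a rule, this SAP should cite it.

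**Conclusion.** The point holds in limited form. Followed exactly, the SAP counts a persisting antibody from earlier exposure as a positive under the new regimen. This can occur in arm 3 and in the previously exposed part of arm 4. It arises chiefly in the restart-only presentation, and in both presentations for antibodies formed in phase 2.

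The size is unknown. Exposure before restart is certain for the planned minimum of 10 patients in arm 3; the number in arm 4 is not stated, and no antibody prevalence is given. A reader might infer that many patients are affected, or that the reported count will be inflated. The documents support neither: they establish that carry-over can be counted, not that it will be.

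The matter goes beyond missing detail because the stated rule itself produces the ambiguous number, while the samples, titres and baseline definition needed for a clearer one are already in the plan. No confirmatory conclusion is affected.

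**What to change.** In SAP section 5.6.3 and Appendix 2:

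1. Keep the existing count and the listing of positives.
2. Add a treatment-emergent count: negative at the section 5.1 baseline, taken as the last sample before the first dose of the new regimen, and positive afterwards. The denominator is patients negative at that baseline with at least one later sample. For patients dosed before the pause, do not use the section 5.1 fallback to a value from before the initial regimen, because it precedes the exposure in question; report them as baseline unknown.
3. Report baseline-positive patients separately, including any titre increase by a factor fixed in advance, with denominators.
4. Split arm 4 by earlier concizumab exposure.
5. If arm 1 data on concizumab are included, apply the same rule from visit 9a. The flowchart shows a visit 9a sample for all arms, while protocol section 9.4.7 restricts main-part samples after screening to arms 2-4; confirm which applies to arm 1.
6. Reconcile the three time frames: Appendix 2 (arms 2-4, after restart only), SAP Table 1 (two data sets, one including the initial regimen) and the protocol endpoint (pre-pause period and arm 1 extension included).

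If a rule already exists in another document, cite it instead. The cost is SAP wording and one extra table, with no new samples.
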